6.1 Schedule of Activities

Table 1: Schedule of MHAPPS Trial Activities

	Aim 1: Timepoint 0	Aim 2: Time Point 1: 0 weeks	Aim 2 Time Point 2: 0-2 weeks	Aim 2 Time Point 3: 1 week – 6 months	Aim 2 Time Point 4: 6 months
Timepoints are relative to each study participant.					
Aim 1 Informed Consent/Assent and Survey	X				
Aim 2 Informed Consent/Assent and Enrollment		X			
Aim 2 Baseline Survey & Contact Sheet		X			
Randomization		X			
Phone call with Idaho Suicide Prevention Hotline (Hotline)			CC+ arm only		
Caring text messages (11 total) sent from Hotline				X	
Aim 2 Outcome Survey					X
Safety Outcomes Reporting			X	X	X

MHAPPS Trial Protocol

SLHS Applied Research

December 30,2020

[figure not shown]

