9.1 Caring Contacts with Introductory Call (CC+)

Caring Contacts will consist of one introductory phone or video conversation to establish a connection between the study participant and the follow-up specialist. The introductory phone call will be unscripted, but will generally include the following elements: an introduction, if appropriate (based on participants' survey scores) a safety/wellbeing check, a review and discussion of the elements of mental distress on which the participant scored highest, a discussion of any relevant resources that may be helpful to the participant, and a description of what to expect with the caring text messages that will

follow. Hotline follow-up specialists will attempt to complete the phone call over a two-week period following study enrollment. If the phone call cannot be completed in two weeks, the Hotline will initiate the text message portion of the intervention.

The call will be followed by a series of 11 personalized caring contacts sent over the course of 6 months via text message or email.¹¹² The frequency and cadence of caring text messages will be consistent for all participants and was determined following consultation with PLES Advisors to ensure it is culturally and age appropriate. Caring text messages will be sent using a HIPAA-compliant program called Mosio according to the following schedule: weeks 1, 2, 3, 4, 6, 8, 10, 12, 16, 20, and 24. While there is no expectation that participants respond to the text messages, some participants may choose to respond. Hotline Follow-Up Specialists will review incoming text messages and phone calls from study participants and will respond according to the Hotline's internal operating procedures. These additional contacts will take place outside of the structured study protocol and will not be under the purview of SLHS institutional policies. Mosio will track the number and content of individual responses to study text messages, and this information will be shared with the study team. Response and ongoing contacts as part of the Hotline's processes will not alter the timing or frequency of caring contacts established by the study protocol. Data collected and stored in Mosio will become part of the study dataset and may be analyzed as part of process evaluation or other analyses.

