9.2 Caring Contacts without an Introductory Call (CC)

Participants will be sent caring text messages according to the schedule above. No introductory phone or video call from the Hotline will be made.

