11.4 Adverse Events and Serious Adverse Events

This protocol does not include tracking of adverse events (AEs). This protocol does not include real-time tracking of serious adverse events (SAEs) for several reasons. First, as stated above, the most important events that would be defined as SAEs are expected safety outcomes in the context of study participants experiencing suicidality or other forms of mental distress. All deaths of study participants will be reviewed and assessed to determine whether the cause of death is suicide. We do not anticipate any SAEs beyond those listed as safety outcomes above, but unanticipated SAEs that occur will be reviewed by the DSMB and the IRB. Second, this research compares two models of an evidence-based intervention that has been widely studied, has an established safety record, and is already in widespread

clinical practice. This is not an experimental, novel, or untested intervention with unknown safety outcomes. Finally, the most important safety question to ascertain in the context of this trial is whether rates of safety outcomes or SAEs are differential across the two intervention groups. This protocol will monitor safety outcomes collected at 6 months as part of routine study outcome assessments through regular DSMB meetings to ensure equal ascertainment of outcomes across intervention groups. This is the most valid and reliable way to review safety data in the context of this pragmatic clinical trial.

12. Data Collection & Management

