7.2.4 Safety analysis

The number and proportion of subject experiencing the listed safety events, as well as any other reported safety events, will be summarized by cohort and treatment arm.

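### SAP 7.2.4 tabulates safety events by arm without regard to source, although only CC+ has a scheduled Hotline call during follow-up: a plausible but probably small ascertainment risk

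*SAP*

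**What the plan says.** SAP 7.2.4 plans counts and proportions for the listed safety events, "as well as any other reported safety events", all by cohort and arm. It names no source or reporting window and no separate display for events that reach the study team by different routes. SAP 6.4 lists the safety outcomes, has them assessed at 6 months, and has the DSMB judge whether their rates differ by arm.

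Protocol 11.4 does not track adverse events and does not track serious ones in real time. It calls a difference between arms the main safety question and describes its method as follows: "This protocol will monitor safety outcomes collected at 6 months as part of routine study outcome assessments". The stated purpose is "to ensure equal ascertainment of outcomes across intervention groups".

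Protocol 9.1 gives CC+ an unscripted introductory call, attempted over the two weeks after enrollment, which may contain "if appropriate (based on participants' survey scores) a safety/wellbeing check". For CC, Protocol 9.2 says: "No introductory phone or video call from the Hotline will be made". On later text contact, Protocol 9.1 says: "Mosio will track the number and content of individual responses to study text messages, and this information will be shared with the study team". Table 1 of the protocol marks safety reporting in the 0-2 week column, where the CC+ call also sits, and again from week 1 to month 6 and at 6 months.

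**The concern.** A by-arm comparison of event rates is fair only if an event has the same chance of being recorded in either arm. The 6-month survey meets that condition by design. The summary in SAP 7.2.4 is wider: it takes whatever is reported, and the schedule allows reporting from the first weeks. The arms differ in planned live contact during that time.

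If events disclosed on the CC+ call, or in text exchanges that the call encourages, enter the table, CC+ could show more events simply because more were heard of. The bias would run against CC+, on the comparison that the protocol treats as its key safety question.

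**Working it through.** The plan gives no event rate or ascertainment figure, so there is nothing to reproduce. The check first compares the reporting routes, then bounds the effect under stated assumptions.

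**Routes by which an event could become known**

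| Route | CC+ | CC |
|---|---|---|
| 6-month outcome survey (Protocol 6, 11.4) | yes | yes |
| Vital records, deaths (Protocol 8.3.1, Table 2) | yes | yes |
| Hotline contact after a high C-SSRS score on the Aim 1 or outcome survey (Protocol 6.2, 16.2.3) | same rule | same rule |
| Incoming texts and calls reviewed by the Hotline (Protocol 9.1) | open | open |
| Scheduled introductory call (Protocol 9.1, 9.2) | yes, safety check conditional | none |

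Only the last route differs by design. The C-SSRS contacts follow either the Aim 1 survey, before randomization, or the outcome survey, so they do not replace the call for CC participants between those points.

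**Inputs**
- r = 0.70, the minimum retention in Protocol 13.2 and SAP 5. Assumption: the survey captures every event in those retained.
- n = 165 per arm per stratum, so 2 x 165 = 330 per arm over both strata.
- p = true event risk, equal in both arms. Assumption: 4%.
- h = share of the events missed by the survey that is heard of through the Hotline in CC+ only. Assumption; the documents give no value.

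**Formula**
- Expected recorded events: CC = n p r; CC+ = n p [r + (1 - r) h].
- Apparent risk ratio = 1 + (1 - r) h / r, which does not depend on p.

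**Call alone**
- Assume events are uniform over 26 weeks. A call at the end of week 2 can reveal at most h = 2/26 = 0.077.
- Ratio = 1 + 0.30 x 0.077 / 0.70 = 1.03.
- 330 per arm: CC = 330 x 0.04 x 0.70 = 9.24; CC+ = 330 x 0.04 x (0.70 + 0.30 x 0.077) = 9.54. The difference is 0.30 events.
- 165 per arm, as SAP 7.2.4 summarises by cohort: 4.62 against 4.77, a difference of 0.15.

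Under uniform events and r = 0.70 this is a ceiling: every call is completed, every earlier event is disclosed and logged, and this includes everyone later lost to follow-up. Better retention shrinks it. With an assumed r = 0.85 the ratio is 1 + 0.15 x 0.077 / 0.85 = 1.01.

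**If more is heard in CC+ than the call alone could yield**

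| h (assumed) | Ratio | Events at 4%, 330 per arm (CC 9.24) | Events at 4%, 165 per arm (CC 4.62) |
|---|---|---|---|
| 0.10 | 1.04 | 9.6 | 4.8 |
| 0.25 | 1.11 | 10.2 | 5.1 |
| 0.50 | 1.21 | 11.2 | 5.6 |

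These values need either substantially more text disclosure in CC+ or events concentrated in the first two weeks. The documents support neither.

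**The case against.** The strongest reply is that there is no conflict to resolve. Protocol 11.4 claims equality for outcomes collected at 6 months, and the call does not change that survey. Protocol 12.1 says study data come from online surveys. Under Protocol 12.2 the Hotline records contact attempts and completed contacts, not events. Protocol 9.1 treats further exchanges as lying outside the study procedures and offers the text-platform data for process evaluation or other analyses. Both arms receive the same 11 messages and can reply or call. SAP 7.2.4 is descriptive, with no test. Read plainly, its open-ended category means events outside the SAP 6.4 list, so an attempt disclosed on the call would count as a listed event and not enter through that phrase. Finally, removing genuine listed events from every comparison would lose safety information.

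Most of this stands. A reader might infer that the SAP disproves the protocol's equal-ascertainment statement, or that ascertainment is known to be unequal. The documents support neither: the SAP goes beyond the 11.4 rationale without contradicting it, and no section says that call disclosures are logged as safety events. That CC+ participants would reply to texts more often is also only an inference.

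Two things remain. SAP 7.2.4 restricts neither the listed nor the other events by source, and Table 1 provides for safety reporting well before 6 months, so the route is open even if unplanned. And although the table is descriptive, Protocol 11.3 and SAP 6.4 ask the DSMB for a judgment about differences between arms.

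**Conclusion.** The point holds as a plausible and probably small ascertainment risk that the SAP could close cheaply. The direction is against CC+. The size is about 1.03 for the apparent risk ratio from the call alone, or 0.3 of an event over 330 per arm at an assumed 4% risk. This rests on equal true risk, events uniform over 26 weeks and 70% survey capture. Under those assumptions a larger effect needs text replies to differ by arm as well. Ratios up to 1.21 follow only from assumed disclosure rates and should not be read as an estimate.

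One limit applies. The calculation describes a table that includes the 6-month survey. Protocol 16.15.1 has the DSMB meet three months after enrollment begins, before any outcome survey can fall due (6 months less 4 weeks). Protocol 11.3 mentions a 3-month assessment, but Table 1 shows no 3-month survey and SAP 6.4 names 6 months only. These sections need to be reconciled. Unless a 3-month source exists, non-fatal events seen at that meeting would come mainly from passive reports, and the documents give no basis for sizing the effect there.

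**What to change.** In SAP 7.2.4:

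1. Record source and date for every safety event.
2. Make the main by-arm comparison the listed events from sources common to both arms: the 6-month survey and vital records. Confirm that the survey asks about the three hospitalization outcomes, since protocol Table 2 names no instrument for them.
3. Show events learned through Hotline calls, text replies or spontaneous report in a separate by-arm table, split by source.
4. Keep an all-source table for the DSMB as supportive, with a note that ascertainment may differ by arm.

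The cost is SAP wording, one data field and an extra table. The downside is that some genuine events, such as an attempt disclosed by text by someone later lost to follow-up, would appear only in the supportive tables. The all-source table keeps them in the DSMB's view. No study procedure changes.

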7.3 HANDLING OF MISSING DATA

Hot deck imputation will be used to account for missing 6-month outcomes. The 6-month outcomes will be sampled from complete cases on the same treatment arm, baseline loneliness score tertile, and study population. This method avoids making parametric

assumptions about the outcome distribution and preserves the relationship between measures (Andridge and Little (2010)). Twenty complete data sets will be imputed and Rubin's rule will be used to pool the results (Rubin 10987).

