6.2 Secondary endpoints

- Secondary outcomes include suicide ideation; suicidal ideation and behavior will be measured as score at 6 months using the Columbia Suicide Severity Rating Scale (C-SSRS). Scores range from 0-6. Risk factors for suicide will be measured by the Interpersonal Needs Questionnaire (INQ-15). This survey measures feelings of perceived burdensomeness and thwarted belongingness; scores range from 15 to 105. The changes from baseline thwarted belongingness and perceived burdensomeness scales will be analyzed separately.
- Depression will be measured as score at 6 months in the Patient Health Questionnaire-9 (PHQ-9); this questionnaire results in a score between 0-27, with higher scores indicating worse depression. A score of 5-9 is considered minimal depression, 10-14 is considered mild major, 15-19 is moderate major, and ≥ 20 is severe major. Analysis will be based on the continuous score, with categories examined in exploratory/sensitivity analysis.

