7.2.1 Primary analysis

The effects of the intervention will be modeled separately in patients and providers/staff. **Linear regression with robust standard errors will be used to determine whether the primary outcome differs between CC+ vs CC**, adjusting for the baseline score as a precision variable. Multiple imputation will be used to account for missing data (see 7.3).

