7.2.2 Secondary analyses

All outcomes will be modeled separately in the patient and provider/staff populations. Linear regression will be used to estimate the difference in means for continuous outcomes; for binary outcomes, GLM models with an identity link will allow for the estimation of the difference in proportions. Robust/sandwich standard errors will be used to allow for departures of the observed standard errors from classic model assumptions.

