7.2.3 Subgroups

The primary outcome will be summarized in subgroups defined by:

- Age category: older adult (50+) vs. adult (26-49) vs younger adult (18-25) vs adolescent patients (<18),
- types of providers (patient-facing providers [physicians and APP; pharmacy, PAS, lab, specialists, technicians, MAs;; nursing; social support services] vs. non-clinical [office work and educators; senior management; and other]),
- baseline suicide risk (low baseline C-SSRS score vs moderate to high baseline C-SSRS score),
- Hispanic vs non-Hispanic,
- female vs male sex at birth,
- cisgender vs transgender or gender-nonconforming,
- heterosexual vs. homosexual, bisexual, or other, and
- urban vs rural.

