7.4 SENSITIVITY ANALYSIS

If the proportion of missing 6-month outcomes is greater than 10%, we will assess the sensitivity of the primary results to a variety of possible missingness generating models (Cro et al. 2020). Sensitivity analyses will explore the possibilities that missing data is more likely to reflect poor outcomes or the missing data mechanism varies by treatment arm. A tipping point analysis will be included.

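### SAP 7.3 draws all 20 hot-deck data sets from one fixed donor pool, so the primary standard error can be up to about 6% too small at 30% missing (minor)

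*SAP*

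**What the plan says.** SAP 7.3 specifies the imputation: "The 6-month outcomes will be sampled from complete cases on the same treatment arm, baseline loneliness score tertile, and study population". Twenty completed data sets are pooled by Rubin's rule. The stated reasons for the method are that it needs no parametric model for the outcome and that it "preserves the relationship between measures".

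SAP 7.2.1 refers to 7.3 for the primary test, a linear regression of 6-month loneliness on arm, adjusted for baseline, with robust standard errors, run separately in each population. SAP 7.2.2, on secondary analyses, says "All outcomes will be modeled separately in the patient and provider/staff populations" but mentions neither missing data nor 7.3.

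SAP 7.4 applies when more than 10% of 6-month outcomes are missing: "we will assess the sensitivity of the primary results to a variety of possible missingness generating models". Protocol 13.4 leaves the imputation technique open, describes multiple imputation as carrying the uncertainty of the imputed values into the estimates, and promises to test sensitivity to the imputation approach and its variables. The power statement (SAP 5, Protocol 13.2) assumes at least 70% retention.

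**The concern.** Rubin's rule gives a correct variance only if the imputations differ from one another by as much as our ignorance of the missing values warrants. There are two sources of that ignorance: which value a person would have had, given the outcome distribution in the cell, and what that distribution is. Drawing repeatedly from the same complete cases reflects the first and treats the second as known. The between-imputation variance is then too small, confidence intervals are too narrow, and the 5% test rejects too often. Because this sits in the primary analysis, the error falls on the main result in each population.

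**Working it through.** **The plan's own figure.** Inputs: 165 per arm per population, 70% retained, 5 units, 80% power (SAP 5, Protocol 13.2); two-sided 5% (Protocol 13.1). Retained: 165 × 0.7 = 115.5 per arm. The SD that gives 80% power is 5 / [(1.960 + 0.842) × √(2/115.5)] = 13.56. The documents state no SD, so the 80% can be shown to fit that value but not checked. It is used here only to set 30% as the largest planned missing share; what follows is in SD units.

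**Closed form.** Take one arm with missing share f, M = 20 imputations, and cells unrelated to the outcome. In units of σ²/n:
- within-imputation variance: 1
- between-imputation variance with fixed donors: f
- Rubin total: 1 + (1 + 1/M)f
- true variance of the pooled estimate: 1/(1 − f) + f/M

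| f | Rubin total | True | SE ratio | Actual size of a 5% test |
|---|---|---|---|---|
| 0.1 | 1.105 | 1.116 | 0.995 | 5.1% |
| 0.2 | 1.210 | 1.260 | 0.980 | 5.5% |
| 0.3 | 1.315 | 1.444 | 0.954 | 6.1% |

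The last column is 2[1 − Φ(1.96 × ratio)]. At 30% missing, the pooled SE is what 165/1.315 = 125.5 observed outcomes per arm would give, although only 115.5 were observed.

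**What is omitted.** With many imputations the gap is 1/(1 − f) − (1 + f) = f²/(1 − f); at f = 0.3 that is 0.09/0.7 = 0.129. Resampling the donors adds exactly this: 1.3 + 0.129 = 1.429 = 1/0.7. The SE rises by √(1.429/1.3) = 1.048, about 5% (2% at f = 0.2, 0.5% at f = 0.1). Since f²/(1 − f) curves upward, uneven missing shares across tertiles make the gap larger for the same average.

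**Simulation of the planned analysis at 30% missing.** 165 per arm, arm-by-tertile cells, baseline-adjusted regression with robust SE, 20 imputations, no true effect. The baseline-to-6-month correlation is an assumption. Set A has 16,000 trials per case (error about 0.2 points on type I error); set B has 6,000 to 8,000 (error 0.8 to 0.9 points on the SE ratio). Random dropout:

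| Correlation | SE ratio as written (A, B) | Type I error as written (A, B) | With donor resampling (A, B) |
|---|---|---|---|
| 0 | 0.936, 0.955 | 6.6%, 6.4% | 5.3%, 5.1% |
| 0.3 | 0.955, 0.958 | 6.3%, 6.3% | 5.1%, 5.0% |
| 0.5 | 0.948, 0.966 | 6.2%, 6.0% | 5.2%, 4.9% |
| 0.6 | not run, 0.973 | not run, 5.8% | not run, 4.9% |
| 0.7 | 0.974, 0.986 | 5.4%, 5.3% | 4.3%, 4.6% |
| 0.8 | not run, 1.009 | not run, 5.0% | not run, 3.9% |

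A third set gave ratios of 0.946, 0.961 and 1.001 at correlations 0, 0.5 and 0.7. The shortfall fades at high correlation because tertile cells discard baseline information within the tertile, which widens the reported SE and offsets the omission.

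With dropout rising with the baseline score (set B, correlations 0.3, 0.5, 0.7), the ratios are 0.935, 0.940 and 0.954 and type I error is 7.2%, 7.0% and 6.7%. Resampling gives 5.5%, 5.1% and 4.5%, with an SE about 7% larger.

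**Less missing data (set A).** At 20%: ratio 0.98 to 1.00, type I error 5.2% to 5.5%. At 10%: 0.99 to 1.01 and 4.6% to 5.4%. Set B gave 0.973 at 10% and correlation 0, but the complete-case analysis of the same samples was off by nearly as much (0.1163/0.1185 = 0.981), so most of that is simulation noise.

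**The case against.** - **The size depends on an unknown.** A reader might take 3% to 6% as a fixed property of the plan. The documents give no baseline-to-6-month correlation. At 0.8 with random dropout there is no shortfall, and resampling then makes a calibrated test conservative. This stands, and the size must be stated conditionally.
- **30% missing is a floor on retention, not a forecast.** A reader might infer that the primary test is materially inflated at whatever retention is achieved. The figures at 10% and 20% missing do not support that. This stands.
- **A competent analyst might resample donors unprompted.** That is possible, and the SAP cites a review of hot-deck methods. But the SAP should state the step that makes the variance right, and 7.3 does not.
- **Scope.** A reader might infer from the silence of 7.2.2 that it is open whether secondary endpoints are imputed. The SAP largely answers this: 7.3 speaks of 6-month outcomes in the plural, its aim of preserving relationships makes sense only for several outcomes, and SAP 5.3 evaluates primary and secondary endpoints in the same intention-to-treat population. What is missing is a cross-reference.
- **Secondary endpoints.** A reader might infer that PHQ-9, C-SSRS and INQ results will be biased, because the cells hold no baseline score but loneliness. Bias arises only if dropout depends on the outcome's own baseline differently by arm. With assumed odds ratios per SD of 2 in one arm and 1 in the other, 30% missing, and assumed correlations of 0.6 (own baseline to 6 months) and 0.5 (loneliness to own baseline), it is 0.09 SD with 9% to 12% false positives. With an odds ratio of 2 in both arms there is essentially none (0.003 SD). The documents support none of these values, and shared cells serve an aim that the SAP states.

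**Conclusion.** The point holds in limited form, and it is minor. As written, SAP 7.3 leaves donor uncertainty out of Rubin's variance for the primary analysis. The understatement of the SE reaches about 6% only near the 70% retention floor, and only if the baseline-to-6-month correlation is about 0.6 or less or dropout rises with the baseline score. The same understatement applies separately in the patient and provider/staff analyses. The estimates rest on simulated outcomes, an assumed correlation range of 0 to 0.8, and analysts adding no unstated step. They do not show bias in the primary estimate, and they do not establish a fault in the secondary endpoints beyond the missing cross-reference.

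**What to change.** 1. **SAP 7.3.** Add that, before each of the 20 imputations, the complete cases in each arm, tertile and population cell are resampled with replacement to their original number, and missing outcomes are drawn from that resampled set (approximate Bayesian bootstrap). Keep the existing cells, which hold about 165 × 0.7 / 3 = 38.5 donors each at 30% missing. Resample participants rather than single values, so that the aim of preserving relationships between measures is kept.
2. **SAP 7.2.2.** Add a cross-reference to 7.3.
3. **Optional.** As a sensitivity analysis under Protocol 13.4, impute each secondary outcome in cells built on its own baseline in place of the loneliness tertile. This should not replace the main approach: donors could then differ between outcomes, which weakens the relationships that 7.3 sets out to preserve.

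**Cost.** A sentence or two and a few lines of code; no new data. Primary intervals become about 5% wider at 30% missing, 2% at 20% and 0.5% at 10% (about 7% at 30% if dropout rises with baseline). The test becomes slightly conservative, about 4%, if the correlation is 0.7 or higher. If the power statement counts retained participants only, as 165 × 0.7 suggests, the wider interval is the one it already assumes.
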